Day 43-50/Visit 4: Subjects will be asked to withhold morning dose of the study drug the day of the study visit. Women of child bearing potential will have a negative pregnancy test confirmed. Subjects will be asked to complete an ACT to assess asthma control and a validated asthma quality of life questionnaire (Juniper mini AQLQ). FeNO will be measured using a Circassia Niox Vero machine with disposable filters. Basic spirometry will be performed, Methacholine test will be performed if subject meets safety criteria ($FEV_1 > 1.5L$ or 60% predicted). 10ml of blood will be collected for measurement of cytokines, biomarkers and blood eosinophil count. For those patients in PK group, an additional 35 ml of blood will be collected over an additional 7 times points (pre-dose, 0.5 hour, 1 hour, 2 hour, 3 hour, 4 hour, and 8 hour). Study drug will be administered in the clinic after the pre-dose PK blood draw.

Unused study medication will be collected and pill count will be recorded.

Day 71-78/Visit 5: Subjects will be asked to withhold morning dose of the study drug the day of the study visit. Women of child bearing potential will have a negative pregnancy test confirmed. Subjects will be asked to complete an ACT to assess asthma control and a validated asthma quality of life questionnaire (Juniper mini AQLQ). FeNO will be measured using a Circassia Niox Vero machine with disposable filters. Basic spirometry will be performed. Methacholine hyperresponsiveness will be measured if subject meets safety criteria ($FEV_1 > 1.5L$ or $>60\%$ predicted). 10ml of blood will be collected for measurement of cytokines, biomarkers and blood eosinophil count. For those patients in PK group, an additional 35 ml of blood will be collected over an additional 7 times points (pre-dose, 0.5 hour, 1 hour, 2 hour, 3 hour, 4 hour, and 8 hour). Unused study medication will be collected and pill count will be recorded. Study drug will be administered in the clinic after the pre-dose PK blood draw.

Sample Size and Population

Adults 18 and older, with physician diagnosed mild to severe persistent asthma will be screened. 36 participants will be randomized equally into two arms (18 per group); 1 gram of oral ginger extract twice a day for 28 days or matching placebo. Our sample size analysis requires 16 participant per group and with an anticipated 10% attrition rate, we will enroll 18/group.

Randomization will not be stratified in this pilot study.

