Day 43-50/Visit 4: Subjects will be asked to withhold morning dose of the study drug the day of the study visit. Women of child bearing potential will have a negative urine pregnancy test confirmed. Subjects will be asked to complete an ACT to assess asthma control and a validated asthma quality of life questionnaire (Juniper mini AQLQ). FeNO will be measured using a Circassia Niox Vero machine with disposable filters. Basic spirometry will be performed, Methacholine test will be performed if subject meets safety criteria ($FEV_1 > 1.5L$ or 60% predicted). 10ml of blood will be collected for measurement of cytokines, biomarkers and blood eosinophil count. For those patients in PK group, an additional 35 ml of blood will be collected over an additional 7 times points (pre-dose, 0.5 hour, 1 hour, 2 hour, 3 hour, 4 hour, and 8 hour). Study drug will be administered in the clinic after the pre-dose PK blood draw.

Unused study medication will be collected and pill count will be recorded.

Day 71-78/Visit 5: Subjects will be asked to withhold morning dose of the study drug the day of the study visit. Women of child bearing potential will have a negative pregnancy test confirmed. Subjects will be asked to complete an ACT to assess asthma control and a validated asthma quality of life questionnaire (Juniper mini AQLQ). FeNO will be measured using a Circassia Niox Vero machine with disposable filters. Basic spirometry will be performed. Methacholine hyperresponsiveness will be measured if subject meets safety criteria ($FEV_1 > 1.5L$ or $>60\%$ predicted). 10ml of blood will be collected for measurement of cytokines, biomarkers and blood eosinophil count. For those patients in PK group, an additional 35 ml of blood will be collected over an additional 7 times points (pre-dose, 0.5 hour, 1 hour, 2 hour, 3 hour, 4 hour, and 8 hour). Unused study medication will be collected and pill count will be recorded. Study drug will be administered in the clinic after the pre-dose PK blood draw.

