6.2.1 Screening Evaluation

Adults 18 and older, with physician diagnosed mild to severe persistent asthma will be screened. After reviewing and signing informed consent, subjects that fulfill inclusion and exclusion criteria will be invited to participate.

Consenting Procedure

Single informed consent describing screening and study procedures.

The study PI ([name]) or the research study coordinator ([name]) will conduct the consent process.

[name] is a professor of medicine and pulmonologist and director of the John Edsall-John Wood Asthma Center at Columbia University Medical Center. [name], B.S. has over 3 years of experience as a clinical research coordinator and has experience consenting and studying pulmonary

patients during clinical studies in the John Edsall-John Wood Asthma Center.

Any changes in the consent form will only occur after approval from the institutional IRB and the NCCIH.

Documentation of the consent process and consent forms will be retained in a research study binder.

Screening

Visit 1: Screening Visit

Sequence of events:

- Identify patients that are adults 18 and older with physician-diagnosed mild to severe persistent asthma
- Sign informed consent
- Fulfill inclusion and exclusion criteria
- Review of medical history
- Record Demographics
- Recording of medication use
- Physical exam including vital signs by study MD or NP
- Urine pregnancy test for women of child bearing age
- Scoring on ACT ≤ 19
- Scoring on basic spirometry before and after bronchodilator

Required to be eligible:

- Patients that are adults 18 and older with physician-diagnosed mild to severe persistent asthma
- Signing informed consent
- Fulfill inclusion and exclusion criteria
- Using inhaled corticosteroids with or without inhaled long acting beta agonists or anti-muscarinics.
- Scoring on ACT ≤ 19
- Negative urine pregnancy test for women of child bearing age

Screening must be completed 14-21 days prior to visit 2 during which the ACT score will be confirmed to be ≤ 19 , and the baseline FEV1 is $\geq 60\%$ of predicted (or 1.5L); Baseline methacholine PD20 will be determined at V2 as a subsequent eligibility criterion.

Visit 2; Day 14 to 21:

- Administer ACT. If ACT remains ≤ 19 , proceed . If ACT > 19 consistent with good asthma control, terminate from study.
- Confirm medication washouts (reschedule if not met).
- Spirometry

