6.2.4 Followup Visits

Visit 3 Day 15-22 RANDOMIZATION VISIT

Procedures Performed:

- Administer questionnaires (ACT, QOL, A2WR)
- Review medical history, conmeds, and AEs since the screening visit
- Confirm medication washouts (reschedule if not met)
- Vitals
- Urine Pregnancy Test (if applicable)
- Physical Exam
- Review Randomization Inclusion/Exclusion Criteria
- Baseline GI side effect check list
- Randomize
- Measure Exhale Nitric Oxide (FeNO)

- Pre-dose Spirometry
- Blood draw cytokines, biomarkers and blood eosinophil count
- Pre-dose Pharmacokinetic blood draw for select subjects
- Administer 1st dose of study drug
- Post-Dose Spirometry (1 hr post-study drug dosing)
- Pharmacokinetic blood draw for select subjects (n =8 4 Males & 4 Females) (Time 0.5, 1, 2, 3, 4 & 8 hrs)- **PK Subgroup only.**
- Dispense drug

Visit 3A Day 29-36: Phone contact to answer questions and encourage compliance.

Visit 4 Day 43-50 (Day 28 of study drug):

Procedures Performed:

- Administer questionnaires (ACT, QOL, A2WR)
- Review conmeds, and AEs since V3
- Review study drug compliance (pill count)
- Confirm medication washouts (reschedule if not met)
- GI side effect checklist
- Vitals
- Urine Pregnancy Test (if applicable)
- Physical Exam
- Exhale Nitric Oxide (FeNO)
- Spirometry
- Perform Methacholine Challenge --- reschedule visit if FEV1 is < 60% or 1.5L
- Administer bronchodilator
- Methacholine Recovery Challenge
- Blood draw cytokines, biomarkers and blood eosinophil count
- Pre-dose Pharmacokinetic blood draw--**PK subgroup only.**
- Study Drug Dosing
- Pharmacokinetic blood draw (Time 0.5, 1, 2, 3, 4 & 8 hrs)—**PK subgroup only.**

Visit 4A Day 44-70: Phone or email contact to answer questions and encourage compliance.

Visit 5 Day 71-78 (Day 56 of study drug)

Procedures Performed:

- Administer questionnaires (ACT, QOL, A2WR)
- Review conmeds, and AEs since the previous visit (V4)
- Review study drug compliance (pill count)
- Confirm medication washouts (reschedule if not met).
- GI side effect check list
- Vitals
- Urine Pregnancy Test (if applicable)
- Physical Exam
- Exhale Nitric Oxide (FeNO)
- Spirometry
- Perform Methacholine Challenge --- reschedule visit if FEV1 is < 60% or 1.5 L
- Administer bronchodilator
- Methacholine Recovery Challenge
- Collect Blood for cytokines, biomarkers and eosinophil count
- Pre-dose Pharmacokinetic blood draw--**PK subgroup only.**
- Study Drug Dosing for PK group only

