6.2.5 Completion/Final Evaluation

Visit 5 Day 71-78 (Day 56 of study drug)

Procedures Performed:

- Administer questionnaires (ACT, QOL, A2WR)
- Review conmeds, and AEs since the previous visit (V4)
- Review study drug compliance (pill count)
- Confirm medication washouts (reschedule if not met).
- GI side effect check list
- Vitals
- Urine Pregnancy Test (if applicable)
- Physical Exam
- Exhale Nitric Oxide (FeNO)
- Spirometry
- Perform Methacholine Challenge --- reschedule visit if FEV₁ is < 60% or 1.5 L
- Administer bronchodilator
- Methacholine Recovery Challenge
- Collect Blood for cytokines, biomarkers and eosinophil count
- Pre-dose Pharmacokinetic blood draw--**PK subgroup only.**
- Study Drug Dosing
- Pharmacokinetic blood draw (Time 0.5, 1, 2, 3, 4 & 8 hrs)—**PK subgroup only.**
- Collect study drug.

Any subjects who discontinue the study early will be contacted to determine the reason why. These reasons will be documented in the study binder. If termination occurs to lack of tolerance or adverse events related to the study drug or procedures, protocols for reporting adverse events will be followed as outlined below.

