7.1 Specification of Safety Parameters

- ***Methacholine challenge*** involves the inhalation of an agonist to induce bronchoconstriction and may induce the symptoms of an asthma exacerbation (chest tightness, dyspnea, coughing). The procedure is performed in a closely monitored clinical environment, with availability of bronchodilator. This procedure has been safely used in many previous studies by our group; we will only perform this procedure if the baseline FEV₁ is > 60% predicted.
- ***Bronchodilator*** (albuterol/salbuterol) will be available to be administered if the participant is uncomfortable from the effects of the methacholine challenge test.
- ***GI side effects*** will be assessed at each study visit.
- ***Venous Blood Draw***: Rarely, people faint after blood drawing and therefore will be seated during blood draws. Very rarely, the vein in which the needle has been inserted may become inflamed or infected.

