9. STATISTICAL CONSIDERATIONS

9.1 General Design Issues

We hypothesize that the oral consumption of Pure Encapsulation® ginger extract (2g/day by adult patients with moderate to severe asthma despite normal maintenance medications, will have an improvement in their tolerance to inhaled methacholine or a reduction in lung inflammation over the 56 day treatment period.

This is a randomized, double blind, placebo-controlled design. Patients will have baseline measurements of their pulmonary function and inflammation status and will then be randomized to ginger extract or placebo. The same measurements of pulmonary function and inflammation status will be repeated at 28 and 56 days of ginger or placebo consumption. The durations of 28 and 56 days were chosen because it is hypothesized that the primary benefit of consumption of oral ginger will be an anti-inflammatory effect in

the lung that over time results in improved pulmonary function.

Primary hypotheses: are that the oral daily consumption of ginger will improve the tolerance to inhaled methacholine and/or a reduction in exhaled nitric oxide.

Secondary hypotheses: are that an additional measure of pulmonary function will improve (an increase in baseline FEV1) and/or that secondary measures of inflammation (eosinophilia, asthma associated cytokines) will improve.

Primary outcome measures: The primary outcome measures are methacholine (PD20) and exhaled nitric oxide. These outcomes will be measured at visit 3 (baseline) and visits 4 and 5 (days 28 and 56 of the oral ginger or placebo consumption).

Secondary outcome measures: A clinically significant increase in baseline FEV1 of 100ml. For subjects with eosinophilia (>300 cells/ul) a 32% decrease in blood eosinophils¹⁷, a 40% decrease in serum IL4^{18,19}, a 50% decrease in serum IL5²⁰ or a 75% decrease in serum IL13.²¹

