10.3.4 Protocol Deviations

Protocol deviations will be captured during subject visits. This will occur by questioning of concurrent medications, appropriate washout of asthma-related medications, pill counts and 2 week recall questionnaires. We will also include less than 70% study drug compliance as a protocol deviation. These will be documented on case report forms. Some deviations (e.g. failure to abide by washout criteria) will result in rescheduling of study visits until the washout period is achieved. Deviations will be review monthly during scheduled meetings of Drs. [name], [name] and the research coordinator. Significant deviations (e.g. failure to comply with consumption of ginger or placebo capsules, failure to appear for study visits within the allowed windows) will result in subject removal from the study.

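### Rescheduling the whole of Visit 4 or 5 when FEV1 is below the methacholine floor can make follow-up FEV1 depend on its own value; postponing only the challenge avoids this

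*Combined protocol and SAP*

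**What the plan says.** - **Sections 6.2.4 and 6.2.5 (procedure lists).** At Visit 4 the instruction is "Perform Methacholine Challenge --- reschedule visit if FEV1 is < 60% or 1.5L". Section 6.2.5 repeats it for the final visit: "reschedule visit if FEV₁ is < 60% or 1.5 L". What is rescheduled is the visit.
- **Précis and section 3.** Spirometry is unconditional at both visits. For Visit 4, "Methacholine test will be performed if subject meets safety criteria"; for Visit 5, "Methacholine hyperresponsiveness will be measured if subject meets safety criteria". What is conditional is the challenge.
- **The floor.** Section 7.1 gives percent predicted alone: "we will only perform this procedure if the baseline FEV₁ is > 60% predicted". The précis and section 3 let an FEV1 above 1.5 L or above 60% suffice at Visit 5. The wording in 6.2.4 and 6.2.5 can be read either way.
- **The outcome.** FEV1 is a secondary outcome in section 9.1: "A clinically significant increase in baseline FEV1 of 100ml". Section 9.6 gives no FEV1 analysis. Section 6.2.2 lists a baseline FEV1 without naming its visit, and section 6.2.1 uses the term for Visit 2 ("and the baseline FEV1 is", followed by the floor).
- **Windows.** Under section 10.3.4, "failure to appear for study visits within the allowed windows" is a significant deviation that leads to removal from the study. No section limits the number of reschedules or says whether a rescheduled visit counts under this rule.

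**The concern.** A coordinator whose patient blows a low FEV1 at Visit 4 or 5 can follow 6.2.4/6.2.5 and repeat the visit, or follow the précis and section 3 and complete it without the challenge. On the first course, if the repeat supplies the data, a low FEV1 is replaced by a new draw because it was low. If ginger raises FEV1, placebo readings fall below the floor more often and are replaced more often, so part of a true benefit disappears. A patient who stays low past the window could also lose FeNO, blood and questionnaire data that did not depend on the challenge being safe that day.

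**Working it through.** **Inputs.** The documents give no mean, SD or power for FEV1; the 100 ml criterion is their only FEV1 effect size, so there is no planned figure to reproduce. Assumptions, in percent predicted: mean 70, 75 or 80 before entry selection; between-patient SD 10 or 12; day-to-day SD s of 5, 6.5 or 8; true ginger effect 4 points (100 ml if predicted FEV1 is 2.5 L, since 0.1/2.5 = 4%). That makes 18 combinations. Entry at Visit 2 is gated at the same floor F. Two floors are used:

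- F = 60%, the section 7.1 reading.
- F = 50%, the reading in which 1.5 L also suffices, at an assumed predicted value of 3.0 L (1.5/3.0). At 2.5 L predicted, 1.5 L is 60% and the two readings coincide.

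**Formula.** Let a patient's true follow-up level be m and redraws be independent. The first attempt fails with probability p = Φ((F − m)/s). With one reschedule and the last value kept,

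E(value used) = E(Y; Y ≥ F) + p·m = m + s·φ((F − m)/s).

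The upward shift is therefore s·φ((F − m)/s). Example: F = 60, s = 6.5.

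- Placebo, m = 65: 6.5 × φ(−0.77) = 1.93 points.
- The same patient on ginger, m = 69: 6.5 × φ(−1.38) = 0.99 points.
- The 4-point benefit appears as 4 + 0.99 − 1.93 = 3.06.

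Most patients are further from the floor. Averaging over true levels weighted by P(Visit 2 ≥ F), the combination mean 75, SDs 10 and 6.5 gives shifts of 0.50 (placebo) and 0.26 (ginger). The observed difference is 4 + 0.26 − 0.50 = 3.76, an attenuation of about 6%.

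**Results over the 18 combinations (numerical integration).**

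| Floor and handling | Attenuation of a 4-point difference |
|---|---|
| 60%, one reschedule, last value kept | 2.1–11.0% (median 5.8%) |
| 50%, one reschedule, last value kept | 0.4–5.8% (median 2.1%) |
| 60%, up to three attempts, last value kept | 2.6–15.2% |
| 60%, up to three attempts, never-passers dropped | 2.8–18.0% (Visit 3 baseline) |

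In the last row, a Visit 2 baseline would give 3.1–20.4%. At F = 60%, first-attempt failure is 2.0–13.4% on placebo and 0.6–7.3% on ginger, or 0.4–2.4 and 0.1–1.3 of 18 patients per visit.

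**Cross-check in litres.** Separate assumptions: mean 2.0–2.6 L, between-person SD 0.55 L, visit-to-visit SD 0.10–0.25 L, floor 1.5 or 1.92 L, true effect 100 ml. One reschedule with the last value used leaves 91.9–99.6 ml, an attenuation of 0.4–8.1%.

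**Against sampling error.** With 16 per arm, SE = √2 × s × √(2/16) = 2.5 (s = 5) to 4.0 (s = 8). At F = 60% with one reschedule the bias is 0.021 × 4 = 0.08 to 0.110 × 4 = 0.44 points. Even crossing the extremes, 0.44/2.5 is 18% of one SE.

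**Null case.** With no true effect, p and the shift have the same distribution in both arms, so the expected arm difference is 0.

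**The case against.** The best defence is that the sections fit together: the précis and section 3 are summaries that do not say what follows a failed criterion, and 6.2.4/6.2.5 supply the step, much as Visit 2 allows rescheduling or termination. Sections 6.2 and 10.3.3 also have spirometry done at each visit, recorded on the case report form and kept in source, so the low reading exists, and no section orders it discarded. Section 9.6 states no FEV1 analysis, so the mean difference studied here is supplied by the review.

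Much of this stands. The texts can be reconciled, and the attenuation depends on the rescheduled value being analysed, which no section prescribes. But nothing rules that out, and the literal instruction repeats the visit.

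The size can also be challenged. The windows are seven days (days 43–50 and 71–78) and long-acting anti-muscarinics need at least seven days' washout, so several attempts are unlikely; the one-reschedule rows are the fairer guide. If a low FEV1 persists for days, independent redraws overstate the shift.

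A reader might infer that the rule also inflates within-arm improvement, because Visit 3 has no FEV1 floor. The documents do not support that. Inclusion criterion 3 contains the FEV1 requirement, and eligibility is reviewed again at Visit 3 (sections 6.1 and 6.2.4), so the floor may apply there too.

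**Conclusion.** The concern holds as a minor, conditional point; the change is a cheap improvement. Read literally, 6.2.4 and 6.2.5 allow follow-up FEV1 to be selected on its own value. If rescheduled values are analysed, a true arm difference shrinks by about 2–11% (60% floor) or 0.4–6% (50% floor), with one reschedule and the last value kept. About 15–18% arises only at the extreme of the assumed inputs with up to three attempts. The means, SDs, effect, number of attempts and independence of redraws are all assumptions.

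A reader might go further and infer a spurious ginger benefit or damage to the primary outcomes. Neither follows: the rule treats the arms alike under the null, its direction under a true benefit is conservative, and nothing here establishes bias in PD20 or FeNO. The outcome affected is secondary, in a 36-patient pilot.

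**What to change.** **Sections 6.2.4 and 6.2.5.** Replace the rescheduling of the visit with postponement of the methacholine challenge alone, with washouts and the withheld morning dose repeated for the later attempt. Complete FeNO, spirometry, questionnaires, blood draws and, for the PK subgroup, PK draws and dosing on the attended day.

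**Section 9.6.** State that attended-day values are the Visit 4 and 5 values even when FEV1 is below the floor, with only PD20 taken from the later attempt. Name one FEV1 baseline visit; Visit 3 pre-dose is the natural choice, being the last reading before the first dose and on the same day as baseline FeNO and bloods.

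Under the same model, attended-day values recover the full 4.0-point difference whichever visit is baseline.

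**Cost.** One sentence in each of 6.2.4 and 6.2.5 and two in 9.6. No visit is added, since the present rule already needs a later attempt, and the safety gate is unchanged. The downside is that PD20 may come from a different day than the other measures in about 0–2 patients per arm per visit. That already happens at baseline, where PD20 is measured at Visit 2 and FeNO at Visit 3.

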The primary endpoints are the improved tolerance to the bronchoconstrictive effect (reduced airway hyperresponsiveness) of inhaled methacholine (methacholine PD₂₀) or a reduction in exhaled nitric oxide. The secondary endpoints are a reduction in markers of asthmatic lung inflammation; specifically serum cytokines, eosinophilia, and establishing pharmacokinetic parameters of biologically active components of ginger in adult asthmatics.

Design and Outcomes

A placebo controlled, double blind, randomized clinical pilot study of mild to severe asthmatics treated in a 1:1 ratio with oral ginger 1 gm twice per day or matching placebo. This will occur in the Columbia University Medical Center, The Johns Edsall-John Wood Asthma Center Outpatient Unit, [name].

Screening/Run-In Period Adults 18 and older, with physician diagnosed mild to severe persistent asthma will be screened. After reviewing and signing informed consent, subjects that fulfill inclusion and exclusion criteria will be invited to participate.

Day 0/Visit 1: Screening Visit: review of medical history, recording of medication use, physical exam by study MD or NP, scoring on ACT and basic spirometry before and after bronchodilator. Subjects will then be asked to continue their usual asthma medications for the 14-21 day run-in period.

Day 14-21/Visit 2: Subjects will be asked to withhold appropriate medications (long acting bronchodilator for 36 hours, short acting bronchodilator for 6 hours). Women of child bearing potential will have a urine pregnancy test checked. Checklist for methacholine will be reviewed with patient. If ACT remains ≤ 19 and FEV₁ > 60% predicted, subjects will undergo methacholine bronchoprovocation testing which involves inhaling increasing concentrations of nebulized methacholine until the measured FEV₁ decreases by 20% of the initial value measured after diluent inhalation, defined as the methacholine PD₂₀. If ACT is > 19, consistent with good asthma control, subjects will be terminated from the study.

Day 15-23 (1-2 days following V2)/Visit 3 Randomization Visit:

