Day 14-21/Visit 2: Subjects will be asked to withhold appropriate short and long acting bronchodilators for the appropriate period. Women of child bearing potential will have a urine pregnancy test checked. Checklist for methacholine will be reviewed with patient. If ACT remains ≤ 19 and FEV1 > 60% predicted, subjects will undergo methacholine bronchoprovocation testing which involves inhaling increasing concentrations of nebulized methacholine until the measured FEV1 decreases by 20% of the initial value measured after diluent inhalation, defined as the methacholine PD20. If ACT is > 19, consistent with good asthma control, subjects will be terminated from the study.

Day 15-23 (1-2 days following V2)/Visit 3 Randomization Visit:

If ACT remains ≤ 19, subjects will be randomized into one of two treatment groups; oral ginger (1g twice per day: Pure Encapsulations™) or matching placebo (*FDA IND in place: # [REDACTED]*). Ratio of randomization will be 1:1.

At the randomization visit women of child bearing potential will have a negative pregnancy test confirmed, subjects will be asked to complete an ACT to assess asthma control and a validated asthma quality of life questionnaire (Juniper mini AQLQ). Fractional excretion of nitric oxide (FeNO) will be measured using a Circassia Niox Vero machine with disposable filters. Pre-dose basic spirometry will be performed. 10ml of blood will be collected for measurement of baseline cytokines, biomarkers and blood eosinophil count. Subjects will be given their first dose of study drug and post-dose spirometry will be repeated one hour later.

A subset of subjects (4 males and 4 females) will undergo pharmacokinetic (PK) measurements of the key metabolites of active ginger components. For those patients, an additional 35 ml of blood will be collected over an additional 7 times points (pre-dose, 0.5 hour, 1 hour, 2 hour, 3 hour, 4 hour, and 8 hour).

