4. SELECTION AND ENROLLMENT OF PARTICIPANTS

4.1 Inclusion Criteria

Subjects must meet all of the inclusion criteria to participate in this study.

1. Adults aged 18 years and above, with mild to severe persistent asthma will be enrolled as defined by The NIH National Asthma Education and Prevention Program (NAEPP) Guidelines for Assessing Asthma Severity¹ (please see table page 9). Subjects will have asthma which is not optimally controlled as defined by Asthma Control Test (ACT) score, despite the current use of inhaled corticosteroids with or without inhaled long-acting beta agonists.
2. Treatment with inhaled corticosteroids (ICS) +/- long acting β -agonists/long acting muscarinics and montelukast;
3. Physician diagnosed asthma, confirmed by patient history/report, as well as pulmonary function test (FEV1 \geq 60% of predicted or 1.5 L) and methacholine testing (Baseline methacholine PD20 < 16 mg/ml if taking ICS or < 8 mg/ml if not taking ICS at Visit 2) to confirm diagnosis.
4. Non-smoker (e.g., tobacco, e-cigarette, marijuana) for \geq 1 yr.; Nicotine patch or gum is allowed.
5. \leq 10 pack-year smoking history;
6. Suboptimal control of asthma as determined by a score < 19 or less on the Asthma Control Test (ACT) at Screening and Randomization Visits.
7. Ability to understand the English or Spanish language and to understand the study procedures and comply with them for the entire study period.
8. Females of childbearing potential: Pregnant or lactating; participants of appropriate age will be screened with urine pregnancy tests at each visit and cannot participate if pregnant. Participants must agree to use effective contraception during the trial.
- 9.

Prior Medical Therapy

Washouts:

The chart below lists medications/substances that decrease airway hyper-responsiveness and should not be taken prior to pulmonary function testing. Withholding times are listed next to the medication.

Medications/Substances	Withhold/Washout Times before test
Caffeine, cola drinks, and chocolate	Avoid the day of
Alcohol	4hrs
Short-acting β -agonists in conventional inhaled doses (e.g. albuterol 200 μ g)	6 hrs
Long-acting β -agonists (e.g. salmeterol)	36 hrs
Ipratropium (Atrovent 40 μ g)	12 hrs
Long-acting anti-muscarinic agents (e.g. tiotropium)	\geq 168 hrs (7days)
Ultra-long-acting β -agonists (i.e. indacaterol, vilanterol, olodaterol) Oral theophylline	24-48 hours (2 days)
Oral theophylline	12-24 Hrs

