- methacholine bronchoprovocation testing if FEV1 is $\geq 60\%$ or 1.5L (reschedule or terminate if $< 60\%$ or 1.5L) to assess baseline methacholine PD20.
- Administer BD for Methacholine Recovery Challenge

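### The FEV1 condition for the methacholine challenge is stated inconsistently: firmly contradictory at Visit 2, ambiguous at Visits 4 and 5

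*Combined protocol and SAP*

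**What the plan says.** **Visit 2.** Section 3 reads "If ACT remains ≤ 19 and FEV1 > 60% predicted, subjects will undergo methacholine bronchoprovocation testing", and the précis sets the same condition. Section 6.2.1 instead lists "methacholine bronchoprovocation testing if FEV1 is $\geq 60\%$ or 1.5L", followed in the same bullet by "reschedule or terminate if $< 60\%$ or 1.5L". The narrative of 6.2.1 just above the Visit 2 list also uses 60% predicted or 1.5 L.

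**Eligibility.** Inclusion criterion 3 (Section 4.1, repeated in Section 6.2) accepts an FEV1 of at least 60% predicted or 1.5 L, and also requires a qualifying methacholine result at Visit 2.

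**Visits 4 and 5.** The précis and Section 3 say, for Visit 4, "Methacholine test will be performed if subject meets safety criteria", and give those criteria as above 1.5 L or 60% predicted; Visit 5 is worded to the same effect. For the same visits Section 6.2.4 says "reschedule visit if FEV1 is < 60% or 1.5L", and Section 6.2.5 repeats this for Visit 5.

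**General safety text.** Section 7.1 says "we will only perform this procedure if the baseline FEV₁ is > 60% predicted", and Section 7 says the same. Neither names a visit or offers a litre alternative.

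No section says which statement governs.

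**The concern.** The challenge deliberately provokes bronchoconstriction in patients selected for suboptimal asthma control, and Section 3 itself calls the FEV1 limits safety criteria. If the limits differ between sections, two staff members following the same protocol can make opposite decisions about the same patient.

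Three things depend on the decision. The first is safety at the test. The second is eligibility, since inclusion criterion 3 cannot be completed without a Visit 2 challenge. The third is the data for PD20, one of the two primary outcomes: the condition decides which values are obtained, delayed or never measured. Section 10.3.4 makes failure to attend within the allowed window a ground for removal, so a rescheduled visit can in principle cost more than a delay. Section 9.6 describes no handling of a missing PD20.

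**Working it through.** There is no planned figure to reproduce. The check codes each statement as a rule on two numbers, FEV1 as percent predicted and FEV1 in litres, and applies it to five illustrative patients. The patient values are assumptions chosen to separate the rules; they do not come from the documents.

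The failure clauses in 6.2.1, 6.2.4 and 6.2.5 are read in two ways:
- Literal: stop if percent < 60 **or** litres < 1.5.
- Shorthand for not meeting the either/or criterion: stop only if percent < 60 **and** litres < 1.5.

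| Statement | Visit | Rule to perform | 55%, 1.8 L | 65%, 1.4 L | 60%, 1.8 L | 55%, 1.4 L | 70%, 2.0 L |
|---|---|---|---|---|---|---|---|
| Précis, Section 3 | 2 | > 60% | no | yes | no | no | yes |
| 6.2.1, perform clause | 2 | ≥ 60% or ≥ 1.5 L | yes | yes | yes | no | yes |
| 6.2.1, failure clause, literal | 2 | ≥ 60% and ≥ 1.5 L | no | no | yes | no | yes |
| 6.2.1, failure clause, shorthand | 2 | ≥ 60% or ≥ 1.5 L | yes | yes | yes | no | yes |
| Précis, Section 3 | 4, 5 | > 1.5 L or > 60% | yes | yes | yes | no | yes |
| 6.2.4, 6.2.5, literal | 4, 5 | ≥ 60% and ≥ 1.5 L | no | no | yes | no | yes |
| 6.2.4, 6.2.5, shorthand | 4, 5 | ≥ 60% or ≥ 1.5 L | yes | yes | yes | no | yes |
| 7, 7.1 | not named | 'baseline' > 60% | no | yes | no | no | yes |

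**Visit 2.** At 55% and 1.8 L the perform clause of 6.2.1 says test; the précis and Section 3 say do not. This needs no choice of reading: same visit, same test, different rule. Sections 7 and 7.1 side with the précis, and at this visit the word 'baseline' gives them little escape, because 6.2.1 itself uses it for the FEV1 confirmed at Visit 2. The same patient meets the FEV1 part of inclusion criterion 3 (1.8 L is at least 1.5 L), but under four of the statements cannot have the test that the rest of the criterion requires.

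**Within 6.2.1.** At 65% and 1.4 L the perform clause says test, and the failure clause read literally says reschedule or terminate. The shorthand reading removes this conflict.

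**Visits 4 and 5.** Read literally, 6.2.4 and 6.2.5 stop both the 55%/1.8 L and the 65%/1.4 L patient, whom the précis and Section 3 test. Read as shorthand, they agree with the précis and Section 3 for all five patients.

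**Boundary.** At exactly 60% and 1.8 L, the précis and Section 3 (Visit 2) and Sections 7 and 7.1 say no; every other row says yes.

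**Action on failure.** It is not stated in the précis or Section 3 for Visits 4 and 5. It is reschedule in 6.2.4 and 6.2.5, reschedule or terminate in 6.2.1, and no test in 7 and 7.1.

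**Agreement.** All rows agree at 70%/2.0 L (test) and at 55%/1.4 L (do not test). The dispute is confined to patients who meet one limit but not the other, or who sit exactly on a limit.

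**The case against.** Three stronger readings are tempting, and the documents do not support them.

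*That 6.2.4 and 6.2.5 flatly contradict Section 3 by demanding both limits.* Section 6.2.1 uses the same pair in one bullet to perform and to reschedule, which suggests that the failure wording is shorthand for not meeting the either/or criterion. On that reading the conflict between 6.2.4 and Section 3 disappears for the patients tabulated, and so does the 65%/1.4 L example. The wording is ambiguous rather than demonstrably contradictory.

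*That Section 7.1 bars patients at or below 60% on the day of Visit 4 or 5.* It speaks of 'baseline' FEV1. Section 6.2.2 lists baseline FEV1 among the study's baseline assessments, while the description of methacholine provocation in Section 6.2 uses 'baseline' for the diluent spirometry of the test itself. If study baseline is meant, 7.1 sets no limit on the value measured at Visits 4 and 5.

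*That PD20 will be missing selectively in the patients with the worst lung function.* Those failing both limits are untested under every statement. The disagreement concerns patients between the limits. Rescheduling delays a measurement and does not in itself lose it; loss requires that the test is still not done within the window, or removal under Section 10.3.4.

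It is also fair to say that FEV1 is not the only protection. The protocol provides a methacholine checklist, a physician or nurse practitioner available, a monitored setting with bronchodilator, and halting at a 20% fall. An entry criterion and a repeat-test condition may also legitimately differ.

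These points narrow the concern. They do not touch the Visit 2 contradiction, the differing boundaries or the differing actions on failure.

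**Conclusion.** The inconsistency is real and nothing elsewhere in the document resolves it. At Visit 2 it is firm: the précis and Section 3 against the perform clause of Section 6.2.1, with Sections 7 and 7.1 worded as the former. At Visits 4 and 5 it is an ambiguity that staff could resolve in opposite ways. It bears on who receives an induced-bronchoconstriction test, who can qualify for the trial, and which PD20 values are obtained or delayed.

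Its size in patients cannot be given. The documents contain no FEV1 distribution, in litres or as percent predicted, and the worked patients show only that the rules diverge. This conclusion assumes that 'or' in the perform clause of 6.2.1 and in inclusion criterion 3 means that either value suffices. It takes no position on which threshold is clinically right.

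**What to change.** The clinicians should reconcile the précis and Sections 3, 6.2.1, 6.2.4, 6.2.5, 7 and 7.1 into one explicit FEV1 condition for each visit at which the challenge is done. Each condition should state:
- whether the two limits are joined by 'and' or 'or';
- whether each boundary is strict;
- which measurement 'baseline' refers to;
- what happens when the condition is not met, including how rescheduling fits with the visit window and the removal rule in Section 10.3.4.

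The result should then be checked for compatibility with inclusion criterion 3 in Section 4.1 and its copy in Section 6.2, so that nobody can meet the FEV1 part and yet be refused the test needed to complete the criterion. The criterion and the test conditions need not be identical.

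Whenever a challenge is not done because of the FEV1 condition, that reason should be recorded so that the analysis can separate these PD20 values from those missing for other causes. The case report forms are not in the text available here, so they may already provide for this.

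The cost is a protocol wording amendment and, if needed, one reason code. Sample size, visit schedule and assessments need not change.
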